8.4. Shift table for selected efficacy endpoints

Shift from baseline to post baseline visits in the categories of ItchyQoL total scores (little, mild, moderate, severe) will be presented based on data with LOCF and as observed.

[REDACTED]	[REDACTED]

9. SAFETY ANALYSES

Safety analyses will consist of data summaries for clinical and laboratory parameters, vital signs, and for adverse events (AEs). Adverse events will be coded using the Medical Dictionary for Regulatory Activities (MedDRA v21.1). Laboratory parameters will be summarized using descriptive statistics, by post-treatment shifts relative to baseline. Vital signs and ECG data will be summarized using descriptive statistics.

9.1. Treatment Exposure

Descriptive statistics will be provided for the following.

- Duration of treatment calculated as [min(last dose date+6, end of study date)-first dose date +1]/7
- Number and percentage of subjects will be tabulated by number of doses (1, 2, 3... and 8). The loading dose is comprised of two injections of maintenance dose.
- Treatment compliance calculated as (100 * number of study doses received/ total planned number of doses on treatment. For early discontinued subjects, total planned doses on treatment will be counted from first dose date to last dose date.

9.2. Adverse Events

Adverse events will be mapped to preferred term (PT) and system organ class (SOC) using the most up to date Medical Dictionary (MedDRA) version 21.1. Treatment emergent AEs (TEAEs) are defined as all AEs started since the first dose date in the treatment period or all AEs occurred in the follow-up period. Furthermore, if an AE cannot be determined as treatment-emergent due to incomplete/missing data, conservatively, it will be considered as treatment emergent and included in the summary tables.

9.2.1. Overall Summary of Adverse Events

The following AE or TEAE summaries will be generated for the safety analysis set.

- Overview of AEs, summarizing number (%) of subjects with any:
 - Any AEs
 - Any TEAEs
 - Drug-related TEAEs
 - Serious TEAEs
 - Drug related serious TEAEs
 - TEAEs leading to dose interruption
 - Drug-related TEAEs leading to dose interruption
 - TEAEs leading to treatment discontinuation
 - Drug-related TEAEs leading to treatment discontinuation
 - TEAEs leading to study discontinuation
 - Drug-related TEAEs leading to study discontinuation
 - Death

9.2.2. TEAEs

- Summary of TEAEs by primary SOC, PT
- Summary of TEAEs by primary SOC, PT, and maximum severity (mild, moderate, or severe)
- Summary of drug related TEAEs by primary SOC, PT

- Summaries of TEAEs presented by PT

9.2.3. Serious TEAEs

The following serious TEAE summaries will be generated:

- Summary of serious TEAE by primary SOC, PT
- Summary of drug related serious TEAE by primary SOC, PT

9.2.4. TEAEs Leading to Dose Interruption

- Summary of TEAEs leading to dose interruption by primary SOC, PT
- Summary of drug related TEAEs leading to dose interruption by SOC, PT

9.2.5. TEAEs Leading to Treatment Discontinuation

- Summary of TEAEs leading to treatment discontinuation by primary SOC, PT
- Summary of drug related TEAEs leading to treatment discontinuation by SOC, PT

9.2.6. TEAEs Leading to Study Discontinuation

- Summary of TEAEs leading to study discontinuation by primary SOC, PT
- Summary of drug-related TEAEs leading to study discontinuation by SOC, PT

9.3. Laboratory Parameters

Blood and urine samples will be collected for clinical laboratory evaluations (including clinical chemistry, hematology, urinalysis, and serology) at the time points specified in Section 0. The data collected in different units will be converted in SI units (the International System of Units) for summary. The following summaries will be provided by laboratory category of chemistry, hematology, urinalysis, and serology.

Laboratory values will be summarized as descriptive statistic for both actual value and change from baseline (post baseline minus baseline) by week. If lab values are recorded as <xx, the limits of xx will be used for summary. If lab values are recorded as TNTC (too many to count), correspondingly maximum values per confirmation by vendors will be used for summary.

Shift table summarizing subject incidence of laboratory normal range (Low, Normal, High) at baseline contrasted with individual visits and minimum or maximum post baseline.

For parameters with bidirectional abnormality (low and high) will be presented by post baseline minimum and maximum.

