  5. Has less than 85% compliance with the daily WI-NRS tool during the last 14 days of the Screening Period prior to randomization, unless approved by the Sponsor.
  6. Has had a significant flare of pruritus and/or skin eruption during the Screening Period (prior to the study drug administration) that requires a medical intervention.
  7. Has any inflammatory, pruritic, and/or fibrotic skin condition other than the diagnosis that defines the cohort unless approved by the Sponsor. For example:
    - a. Has urticarial vasculitis, urticaria pigmentosa, systemic mastocytosis, familial cold urticaria or hereditary or acquired angioedema due to C1 inhibitor deficiency.
    - b. Has a clear cause of urticaria including but not limited to cold, heat, solar, pressure, and delayed pressure. Has contact urticaria, aquagenic urticaria or cholinergic urticaria.
    - c. Has pustular psoriasis, erythrodermic/exfoliative psoriasis, drug-induced psoriasis, or psoriatic arthritis
    - d. Has atopic dermatitis
  8. Has significant severe xerosis that persists despite the regular use of an emollient unless approved by the Sponsor.

9. Has uncontrolled hyperthyroidism or hypothyroidism. Has insulin-dependent diabetes or uncontrolled diabetes defined as hemoglobin A1c >7.5%.
10. Has had cancer or lymphoproliferative disease within 5 years prior to Day 1
11. Has had any autoimmune disorder other those under investigation in this study
12. Has had a severe allergic reaction to any foods or medications including anaphylactic reactions unless approved by the Sponsor.
13. Has had systemic amyloidosis
14. Has had immune deficiency, or opportunistic infections
15. Has positive results for hepatitis B surface antigen (HbsAg)
16. Has positive results for hepatitis B anti-core antibody (anti-HBc) but negative results for anti-surface antibody (anti-HBs)
17. Has positive results for hepatitis C antibody
18. Has human immunodeficiency virus (HIV) infection or positive HIV serology
19. Has psychiatric illness other than stable mild to moderate anxiety and/or depression unless approved by the Sponsor
20. Has been hospitalized for a psychiatric illness
21. Has laboratory abnormalities that fall outside the windows below at the Screening Visit:
  - a. Alanine aminotransferase > 1.5 x Upper limit of normal (ULN)
  - b. Aspartate aminotransferase > 1.5 x ULN
  - c. Gamma-glutamyl transferase > 1.5 x ULN
  - d. Blood bilirubin > 1.25 x ULN

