  - e. Hemoglobin more than 1g/dL below the lower limit of normal for sex per the laboratory in which screening lab is performed.
  - f. Platelet count <120,000/  $\mu$ l
  - g. Creatinine > 1.25 x ULN
22. Has a body mass index (BMI) of <16 kg/m^2 or >38 kg/m^2
23. Has systolic blood pressure above 150 mm Hg, diastolic blood pressure above 95 mm Hg at the Screening Visit or Day 1 (confirmed by repeat measurement).
24. Has been hospitalized within 12 weeks prior to Day 1
25. Has had major surgery within 12 weeks prior to Day 1 or has a major surgery planned during the study
26. Has had an active infection including skin infection, requiring systemic treatment within 4 weeks and/or topical treatment within 2 weeks of Day 1. Has an active or chronic parasitic infection.
27. Has any medical (heart, lung, kidney, liver, metabolic) or psychiatric condition which, in the opinion of the Investigator or the Sponsor, may place the subject at increased risk as a result of study participation, interfere with study participation or study assessments, affect compliance with study requirements, or complicate interpretation of study results.
28. Has received a live attenuated vaccine within 12 weeks prior to Day 1

29. Has previously taken part in or withdrawn from this study or has previously received the study drug. Screen failures may be rescreened at the discretion of the Investigator.
30. Has a known hypersensitivity to KPL-716 or its excipients
31. Has a known history of drug or alcohol abuse in the last 2 years prior to Day 1. Has more than eight drinks (5 ounces of wine, 12 ounces of beer or 1.5 ounces of liquor) weekly for females and 15 drinks weekly for males
32. Has a positive urine drug screen for opiates, opioids, methadone, cocaine, phencyclidine, or amphetamines at the Screening Visit. Exceptions may be made if a subject is on a Sponsor-approved medication for a stable concomitant condition that explains the positive drug screen result.
33. Has received blood products within 8 weeks prior to Day 1
34. Has donated blood within 12 weeks prior to Day 1, platelets within 10 weeks prior to Day 1, or plasma within 6 weeks prior to Day 1

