### **8.7.3 Clinical and Laboratory Events and Analyses**

Continuous laboratory data will be examined for trends using descriptive statistics of actual values and changes from baseline over time. These data will also be categorized as low, normal or high based on the reference ranges of the central laboratory. Shift tables from baseline to each post baseline time point will be presented.

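### Laboratory results are classed only as Low, Normal or High, so no planned table counts, by arm, the subjects whose values worsen substantially

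*SAP*

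**What the plan says.** **Classification.** SAP 9.3 plans descriptive statistics of laboratory values and of their change from baseline by week, and then this: "Shift table summarizing subject incidence of laboratory normal range (Low, Normal, High) at baseline contrasted with individual visits and minimum or maximum post baseline". Protocol 8.7.3 has the same scheme: "These data will also be categorized as low, normal or high based on the reference ranges of the central laboratory". Neither document sets a laboratory category by multiple of the upper or lower limit of normal (ULN, LLN), by toxicity grade, or by marked abnormality.

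**Entry.** Exclusion criterion 21 applies to a subject who "Has laboratory abnormalities that fall outside the windows below at the Screening Visit". Its limits include "Aspartate aminotransferase > 1.5 x ULN", "Gamma-glutamyl transferase > 1.5 x ULN" and "Blood bilirubin > 1.25 x ULN". The ALT limit is also 1.5 × ULN and the creatinine limit 1.25 × ULN. For hemoglobin the exclusion is "Hemoglobin more than 1g/dL below the lower limit of normal for sex", and for platelets it is a count under 120,000/µl. Values outside the reference range but within these limits are therefore admitted.

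**Baseline.** Under SAP 5.2, baseline is the last available value before the first injection. Bloods are drawn on Day 1 before dosing, but the results reviewed at that point are those from Screening (Protocol 4.1.2.1).

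**Other numeric safety data.** SAP 9.4, Table 3 sets numeric limits for vital signs. SAP 9.5 counts QTcF above 450, 470 and 500 msec, and changes above 30 and 60 msec.

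**The concern.** A three-class shift table registers only a crossing of the reference limit. It has no room for worsening in a subject who starts outside the range, and it gives a trivial crossing the same weight as a large one. The entry criteria make an abnormal baseline possible for several hepatic, renal and hematologic measures.

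Safety is a secondary objective and laboratory results are a named safety parameter. Protocol 1.4 accepts that new adverse events may emerge with longer exposure in new disease populations. A reader of the report will want to know how many subjects per arm had a substantial laboratory change, and whether transaminases and bilirubin rose in the same person. As planned, that reader would have to work it out from listings.

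**Working it through.** The documents give no figure for laboratory shifts, so there is none to reproduce. The check applies the written rule to example values. Values are multiples of ULN, and High means above 1.

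**1. The rule applied**

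| Baseline | Post-baseline | Classes | Table entry | Fold change |
|---|---|---|---|---|
| 1.4 | 6 | High, High | no shift | 6 / 1.4 = 4.3 |
| 0.98 | 1.02 | Normal, High | shift | 1.02 / 0.98 = 1.04 |

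The first row holds at each visit and for the post-baseline maximum. It needs no assumption beyond the example values. A start of 1.4 is within the Screening limit for ALT, AST and GGT. For bilirubin and creatinine the same logic applies from any baseline between 1 and 1.25. For hemoglobin it applies in the other direction, from a baseline up to 1 g/dL below LLN. Whether a platelet count of 120,000/µl is Low depends on a laboratory range that the documents do not give.

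**2. Entry limit and baseline are different measurements.** The limits bind at Screening, while baseline is normally the Day 1 sample. A subject who was High at Screening may be Normal at baseline. Equally, a Day 1 baseline may lie above the entry limit. So an abnormal baseline is possible but not certain for any given subject.

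**3. What the mean shows.** One subject rising from 1.4 to 6 changes by 4.6 × ULN. That moves the arm's mean change by 4.6 / 16 = 0.29 × ULN with 16 KPL-716 subjects, or 4.6 / 10 = 0.46 × ULN with 10 placebo subjects. The mean alone would hardly reveal it. The planned minimum and maximum (SAP 5.1) would.

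**4. Shifts from noise alone.** Appendix 1 of the protocol schedules blood tests after baseline at Weeks 2, 4, 6, 8, 12, 16 and 18, which is 7 draws. Assume a subject stable at t × ULN, Normal at baseline, with lognormal and independent within-subject variation. The coefficient of variation (CV) is not in the documents; 10% to 20% is assumed.

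P(High at one visit) = 1 − Φ(ln(1/t) / s), with s = √(ln(1 + CV²)). P(maximum High) = 1 − (1 − P)^7.

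| t | One visit, CV 10% to 20% | Maximum of 7, CV 10% to 20% |
|---|---|---|
| 0.9 | 14.5% to 29.7% | 66.7% to 91.5% |
| 0.8 | 1.3% to 13.0% | 8.5% to 62.3% |
| 0.7 | about 0% to 3.6% | 0.1% to 22.6% |

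The range is too wide to support one expected rate. It shows only that subjects near the limit can fill the shift-to-High cell of the maximum table without any drug effect.

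**The case against.** The strongest reply is that the shift table is not the only laboratory output. SAP 5.1 and Protocol 8.1 define descriptive statistics to include minimum and maximum, and SAP 9.3 applies them to values and changes. A rise to 6 × ULN would normally be the maximum at its visit. SAP 5.1 also has listings generally sorted by treatment group, in cohorts of about 26. Protocol 7.5.2 makes clinically significant findings after Screening adverse events, which SAP 9.2.2 tabulates, and Protocol 7.6.1 provides periodic safety review. All of this stands. It means a reader who infers that a true hepatic or hematologic signal would go unseen is going further than the documents allow. These outputs still do not say how many subjects in each arm newly crossed a given limit, and the adverse event route depends on each investigator's judgement.

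Two other stronger readings also fail.

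- A reader might take the remarks on hematopoiesis and platelet synthesis in Protocol 1.3 and 1.4 as naming a pathway at risk. They say the reverse: KPL-716 does not inhibit that pathway, and this is given as a reason to expect no specific safety concern.
- A reader might put a figure on chance shifts: 1 − 0.975^7 = 16%, or 0.162 × 16 = 2.6 of 16 active subjects per analyte. That is at most an upper bound, under independent draws and a ULN at the 97.5th percentile of this population. The documents give neither. The same arithmetic yields 0.162 × 10 = 1.6 of 10 on placebo, so the control arm already supplies a reference.

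It is also fair to say that protocol and SAP agree with each other here. Nothing is contradicted.

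**Conclusion.** The point holds as a minor one. The three-class rule cannot register worsening from an abnormal baseline, entry permits such baselines, and no planned table counts substantial laboratory changes by arm. The SAP does plan numeric-threshold counts for vital signs and QTcF, so laboratory data fall short of its own practice.

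The classification result follows from the definitions alone. How many subjects it will affect cannot be derived, because the documents do not say how many will have an abnormal baseline, and the noise figures rest on an assumed CV and independent draws. No stated figure is wrong and no efficacy conclusion is touched.

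**What to change.** Keep the shift tables. Before database lock, add to SAP 9.3 one treatment-emergent table by arm that counts subjects who newly cross graded reporting limits:

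- First band at the protocol's entry limits: ALT, AST and GGT above 1.5 × ULN; bilirubin and creatinine above 1.25 × ULN; platelets below 120,000/µl; hemoglobin more than 1 g/dL below LLN.
- Higher bands chosen by the sponsor, for example ALT and AST at or above 3 × and 5 × ULN, and bilirubin at or above 2 × ULN. These are not taken from the protocol. They should be labelled as reporting cut-offs, not clinical rules.
- A rule for newly crossing: a subject counts in a band only if baseline was not already in that band or a worse one. This covers Day 1 baselines beyond the entry limits.
- A cross-tabulation of maximum ALT/AST by maximum bilirubin, by arm.

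The cost is the added programming, from data already collected, with no new test or visit. The downside is one more descriptive table without multiplicity adjustment.

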9.4. Vital Signs and Weight

Vital signs (systolic and diastolic blood pressure, pulse, respiration, temperature) and weight will be summarized in descriptive manner by visit for both actual values and changes from baseline (post baseline minus baseline) for each visit. At any visit and timepoint, if the test is repeated, the average will be used for the analysis at this visit.

All vital signs including weight, pulse rate, body temperature, respiration rate, and systolic and diastolic blood pressure will be summarized. Descriptive statistics will be presented for the observed value and the change from baseline at each scheduled visit, and dose group (active versus pooled placebo). Incidence of clinically relevant vital signs noted post-baseline will also be summarized for each study part and treatment group (active versus pooled placebo). Clinical relevance is based on the following criteria (Table 3).

Table 3: Criteria for Clinically Relevant Vital Signs Post-Baseline

Parameter	Clinically Relevant Criteria
Systolic Blood Pressure (mmHg)	
 • Hypertension: Any post-baseline value of 120-139, 140-159, ≥ 160 • Hypotension: Any post-baseline value ≤ 90 or post-baseline value ≥ 30 decrease from baseline
Pulse Rate (bpm)	
 • Any post-baseline value >100 or ≥ 20 increase from baseline • Any post-baseline value <60 or post-baseline value ≥ 20 decrease from baseline
Respiratory Rate (breaths/min)	
 • Any post-baseline value >24 • Any post-baseline value <10
Body Temperature (°C)	
 • Any post-baseline value ≥ 38 • Any post-baseline value ≤ 36

9.5. Electrocardiograms

Numeric 12-lead ECG parameters will be summarized. Descriptive statistics will be presented for the observed value and the change from baseline at each scheduled visit, route of administration, and dose group (active versus pooled placebo). Incidence of a normal to abnormal shift for overall ECG interpretation will also be summarized as appropriate. Findings of other categorical parameters will be listed. For repeated assessment, if interpretations are the same, the last value will be taken for numerical assessment for summaries. If interpretations are different, the last value with the abnormal interpretation will be used for summary.

For the assessment of QT interval changes from baseline, Fridericia's method was used to correct for heart rate

Below incidence of QTcF shifts from baseline will be summarized by category:

- QTcF interval >450 msec
- QTcF interval >470 msec
- QTcF interval >500 msec

- QTcF change from the baseline (pre-dose) is >30 msec and >60 msec

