### **7.5.4 12-Lead Electrocardiogram**

The 12-lead ECG recording will be performed at the designated time points as outlined [Appendix 1](#).

Resting 12-lead ECGs will be recorded after the subject has been supine and at rest for at least 5 minutes.

Single 12-lead ECGs will be repeated twice if either of the following criteria apply:

- QT interval corrected for heart rate using Fridericia's method (QTcF) interval >450 ms in men and >470 ms in women
- QTcF change from the baseline (pre-dose) is > 60 msec

Additional 12-lead ECGs may be performed at other times if judged to be clinically appropriate or if the ongoing review of the data suggests a more detailed assessment of ECGs is required. The Investigator or designee will perform a clinical assessment of each 12-lead ECG.

Any new clinically significant ECG abnormalities occurring during the study will be recorded as AEs.

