### **8.7.4 ECG Analyses**

For repeated performance of 12-lead ECG, average values will be taken. Descriptive statistics of actual values and changes from baseline over time will be summarized by ECG parameter. For ECG overall interpretation of normal and abnormal, shift tables from baseline to each post baseline time points and worst post baseline will be presented.

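### SAP 9.5 replaces the protocol's averaging of repeated ECGs with an unexplained last or last-abnormal rule, which can move QTcF summaries and outlier counts either way

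*SAP*

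**What the plan says.** Protocol 7.5.4 takes one ECG and adds two more on a trigger: "Single 12-lead ECGs will be repeated twice if either of the following criteria apply". The criteria are a QTcF "interval >450 ms in men and >470 ms in women", or "QTcF change from the baseline (pre-dose) is > 60 msec".

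Protocol 8.7.4 then fixes the value to analyse: "For repeated performance of 12-lead ECG, average values will be taken".

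SAP 9.5 has a different rule with two branches. For repeated assessments, "if interpretations are the same, the last value will be taken for numerical assessment for summaries". If the interpretations differ, "the last value with the abnormal interpretation will be used for summary". The same section lists the QTcF categories, starting at "QTcF interval >450 msec" and continuing with 470 and 500 ms, and then "QTcF change from the baseline (pre-dose) is >30 msec and >60 msec". It does not say whether the repeat rule governs these categories as well as the numeric summaries.

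The SAP introduction names the protocol of 28 January 2019 as its basis. SAP 9.4, the section immediately before, averages repeated vital signs.

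**The concern.** The two documents give different values for the same set of readings, and both rules cannot be followed. SAP 9.5 neither mentions the protocol rule nor says why it was replaced. The averaging of vital signs in SAP 9.4 shows that the SAP has no general policy against averaging.

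The choice matters because repeats are not taken at random. They follow a first reading that was high or far from baseline, so the first of the three is a selected value. The rule decides whether that value is averaged in, kept alone or dropped. Under the SAP this depends on a reader's normal or abnormal label, which is itself an outcome of the ECG.

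The outputs at stake are the numeric ECG summaries and, if the rule covers them, the QTcF category counts. Post-baseline ECGs are scheduled only at Weeks 8 and 18. With about 16 and 10 subjects per cohort, one subject is 1/16 = 6.3% of the KPL-716 arm or 1/10 = 10% of the placebo arm, so one reclassified reading is visible in a table.

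**Working it through.** The documents give no figure for this point, so there is none to reproduce. The check runs the same readings through both rules.

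**Inputs from the documents**
- Three readings x1, x2, x3 when a repeat is triggered (Protocol 7.5.4).
- Protocol value: (x1 + x2 + x3)/3 (Protocol 8.7.4). The protocol does not spell out that the triggering reading is in the average; I take it to be.
- SAP value: x3 if interpretations agree; otherwise the last reading called abnormal (SAP 9.5).
- Interpretation: the overall normal or abnormal reading of the ECG, not a QTcF limit (SAP 9.5).

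**Worked readings (ms, chosen for illustration)**

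| Readings | Interpretations | Protocol mean | SAP value | Counted above 450? |
|---|---|---|---|---|
| 462, 446, 440 | only first abnormal | 1348/3 = 449.3 | 462 | protocol no, SAP yes |
| 470, 446, 440 | agree | 1356/3 = 452.0 | 440 | protocol yes, SAP no |
| 455, 444, 441 | only last abnormal, for a non-QT reason | 1340/3 = 446.7 | 441 | neither; SAP value lower |

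If all three interpretations in the first row agreed, the SAP value would be 440 instead of 462. The label alone moves the result by 462 − 440 = 22 ms.

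If the protocol meant only the two repeats, the mean in the first two rows would be (446 + 440)/2 = 443.0. The SAP value would still be above it in the first row and below it in the second, but the second row would no longer cross 450.

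**Direction over a range.** Assumptions, none of them in the documents: normal readings, mean QTcF 405 to 425 ms, between-subject SD 16 ms, within-subject SD 6 to 12 ms, and repeats triggered by a first reading above 450 ms (the male criterion). With 1,000,000 simulated subjects per setting, the share of triggered sets counted above 450 ms was:

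| Rule | Lowest to highest over settings |
|---|---|
| Protocol mean of three | 28.0% to 72.6% |
| SAP, interpretations agree | 23.1% to 62.5% |
| SAP, abnormal means QTcF above 450 | 100% |
| SAP, abnormal unrelated to QTcF (30% per reading) | 34.3% to 68.1% |

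Setting by setting, the agreeing branch was about 5 to 11 percentage points below the mean. The unrelated-label case ran from about 5 points below it to 6 above. For the limit of 470 ms the SAP rule was higher in every setting (1.6% to 11.7%, against 0.7% to 4.6%), because one reading varies more than a mean of three.

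**How far the size depends on the label.** Take a man with true QTcF 440 ms and independent readings (assumed within-visit SD 8 or 10 ms).
- P(first reading above 450) = 1 − Φ(10/8) = 0.106, or 1 − Φ(10/10) = 0.159.
- If abnormal means QTcF above 450, every triggered set is counted. The SAP flags 10.6% or 15.9% of visits, against 0.9% or 2.5% with the mean.
- If interpretations always agree, the SAP flags 0.106² = 1.1% or 0.159² = 2.5%, against the same 0.9% or 2.5%.

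The large difference comes entirely from the assumption about the label.

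**The case against.** The best defence is that keeping an abnormal reading when interpretations conflict is a familiar cautious choice in safety reporting. It applies alike to both arms, and Protocol 8.7 leaves the detail of safety analyses to the SAP. In the agreeing branch the last reading is also the less biased value. For the man with true QTcF 440 it averages 440, whereas the three-reading mean averages 444.6 to 445.1 in triggered sets because it contains the triggering value.

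The point about bias stands: averaging dampens the selection but does not remove it. The rest does not settle the matter. A general delegation of detail does not withdraw the specific rule in Protocol 8.7.4. The caution also covers only one branch, since the other can discard the high reading that prompted the repeats.

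A reader might infer the stronger claim that the SAP rule inflates QTcF outlier counts. The documents do not support that as a general result. It needs the abnormal label to follow QTcF, which SAP 9.5 does not say, and it ignores the last-value branch, which can lower the count above 450 ms.

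Nor are the QTcF categories the only ECG safety output. SAP 9.5 also plans numeric summaries, an interpretation shift and listings, and Protocol 7.5.4 records new clinically significant ECG abnormalities as adverse events.

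**Conclusion.** The conflict is real and rests on the text alone. Protocol 8.7.4 averages repeated ECGs; SAP 9.5 takes the last or last-abnormal value without explanation. The SAP rule selects a number by a reader label and can change numeric summaries and QTcF counts in either direction.

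The net effect cannot be sized. That would need the frequency of discordant interpretations and their relation to QTcF, and the documents give neither. The simulated percentages rest on assumed QTcF distributions and show direction only. They use the male trigger. A woman between 450 and 470 ms is repeated only if her change exceeds 60 ms, so the comparison at 450 ms concerns mainly men.

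This is a minor point. It touches safety reporting only and leaves the primary endpoint unaffected.

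**What to change.** In SAP 9.5, use the mean of all readings at a visit, including the one that triggered the repeats, for numeric ECG summaries. State that the same rule governs the QTcF categories. Keep an any-abnormal rule only for the overall interpretation shift table.

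If the sponsor prefers the present SAP rule, record it as a change from Protocol 8.7.4, state whether it covers the QTcF categories, and show the averaged result as a sensitivity summary.

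The cost is a sentence or two in the SAP and no new data. The small downside is that an isolated abnormal value is dampened in the summaries, but it stays visible in the listings and the shift table.
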